- All adult subjects over the age of 18 with chronic pain* presenting to the emergency department with exacerbation of their chronic pain as their primary complaint
- Subjects who are willing and able to provide informed consent.
- * Chronic pain defined as greater > 3 months of symptoms and an initial VAS pain score > 70

Exclusion criteria:

History of overt psychosis, severe HTN as defined by SBP > 180 or DBP > 110, unstable angina, CAD, CHF, porphyrias, thyroid disease, seizure disorder, inability to provide informed consent: dementia, non-English/Spanish speakers, subjects in custody, suicidal, or clinically intoxicated.

c) Local Number of Subjects

We look to enroll a total of 106 subjects meeting the study criteria.

Protocol Modification 4/24/2018:

We are requesting the enrollment of an additional 10 subjects to the protocol. We initially asked to enroll 96 subjects and have thus far enrolled 80 and the recruitment has continued on schedule. In recent discussion with our statistician and co-investigator, [name], the original group size analysis of 96 (32 in each of three groups) did not account for potential loss of data or subjects withdrawing from the study and we should have asked initially for 106 subjects with the expectation of a 10% loss of data due to incomplete records or withdrawal of subjects in the study.

Rev. 04/24/2018

d) Study-Wide Number of Subjects*

This is a single center study done at the Harbor UCLA Emergency Department

e) Study Timelines*

Duration of an individual subject's participation in this study is 1 emergency department visit and one follow-up phone contact 24-48 hours after discharge from Emergency Department.

The estimated date for the start of enrollment of subjects will be September 2015, and it will be continued till the enrolled subjects' number reach the goal of 106.

f) Study Endpoints*

Primary endpoint: To compare pain relief between the 3 treatment groups as measured by the VAS. A decrease of at least 20mm on the VAS will be considered "significant" pain relief (20)

Secondary endpoint:

- (a) To compare total dosage of IV hydromorphone needed as rescue therapy to achieved adequate pain relief
- (b) To assess the risk for complications of sub-dissociative dose ketamine

g) Procedures Involved in the Human Research*

- 1. The informed consent process will be initiated by investigators in the emergency department.

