- 13. Subjects will be asked if they require additional pain relief. Those who request further pain relief will be administered hydromorphone IV, the dosage and frequency will be at the discretion of the treating physician. Total hydromorphone administration will be documented on the data collection sheet.
- 14. All subjects will receive a follow-up phone call from one of the investigators between 24 48 hours after their visit to the Emergency Department to gauge the extent of their continued pain through the use of a Pain Rating Scale. They will also be asked if they suffered any untoward effects and if so, will be asked to detail them.
- 15. Any study patient returning to the Emergency Department for any reason will be fully evaluated and the study team will be notified. If there is evidence of any psychotic reaction (persistent or delayed presentation after the administration of the medication, the patients will be treated with benzodiazepines (shown to be effective in the emergence reaction sometimes seen after dissociative doses of ketamine are used) and a psychiatric consult will be obtained. The medical monitor will also be notified because this would be an adverse event.

h) Data and Specimen Banking*

No data collected for banking purposes.

i) Data Management *

Descriptive statistics will be used. Tests for significance will be conducted using the t test for continuous variables and chi-squared test or Fisher's exact test for categorical variables.

We estimated the sample size needed for the primary end point of significant pain relief as defined by a decrease in the VAS of 20mm. A power analysis based indicated that a sample size of 106 subjects would be required to detect a statistically significant difference with a power of 90% ($\alpha = 0.05$).

Data from the patient examinations will be stored in an excel spreadsheet or compatible REDCAP database after being de-identified of all unique information to the subject. The study source documents (including consent forms, etc.) will be stored in a locked filing cabinet in a locked office only accessible by study investigators. It will be stored until this

Rev. 04/24/2018

study completes. The data will be shared among the principal investigator and coinvestigators. Principal investigator will be responsible for receipt or transmission of the data.

Protocol Modification 4/24/2018:

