We are requesting the enrollment of an additional 10 subjects to the protocol. We initially asked to enroll 96 subjects and have thus far enrolled 80 and the recruitment has continued on schedule. In recent discussion with our statistician and co-investigator, [name], the original group size analysis of 96 (32 in each of three groups) did not account for potential loss of data or subjects withdrawing from the study and we should have asked initially for 106 subjects with the expectation of a 10% loss of data due to incomplete records or withdrawal of subjects in the study.

j) Confidentiality

Confidentiality will be maintained by use of coded data sheets and an enrollment logbook. Data will be stored in a password locked excel data sheet s/REDCAP database. The study source documents (including consent forms, etc.) will be stored in a locked filing cabinet in a locked office only accessible by study investigators. It will be stored until the completion of this study. Only research investigators and research associates will have an access to this data or the room where the data sheets and enrollment logbook is kept.

k) Provisions to Monitor the Data to Ensure the Safety of subjects*

[name], an Emergency Physician not associated with the study but who has an expertise in procedural sedation in emergency department patients will be a Safety Monitor who will review all patient information whether they received placebo or ketamine for both harm and benefit on a monthly basis to determine if the study is safe to continue. [name], is an LAbiomed investigator with significant experience in the conduct of research and possesses the expertise to serve as the Safety Monitor.

l) Withdrawal of Subjects*

Subjects will be withdrawn from the study if they don't complete their Ketamine or normal saline infusion and they will continue to be monitored and treated as necessary if they experience any untoward or unexpected effects from the medication.

10) Risks to Subjects*

Risk of Ketamine

Incidence unknown: Bloody or cloudy urine, bluish lips or skin, blurred vision, chest pain or discomfort, confusion, disorientation, convulsions, cough, increased secretions, dizziness, syncope, tachycardia, hives, itching, facial edema, hallucinations, rash, agitation, anxiety, fatigue, unmasking psychosis

Risk of Sodium Chloride

Common: None Uncommon: Edema

Rare: Congestive Heart Failure from fluid overload

Risk of intravenous catheter insertion

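### Does section 9(i) misstate the sample size and power by crediting the power analysis with 106 subjects when the group-size analysis gave 96?

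*Combined protocol and SAP*

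**What the plan says.** The power sentence in section 9(i), Data Management, reads: "A power analysis based indicated that a sample size of 106 subjects would be required to detect a statistically significant difference", with 90% power and alpha 0.05. It describes the target of the calculation as "significant pain relief as defined by a decrease in the VAS of 20mm". It gives no standard deviation, response rates, between-group difference or sidedness, and it does not mention loss of data. The tests named in that section are the "t test for continuous variables and chi-squared test or Fisher's exact test for categorical variables".

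The modification note of 4/24/2018 closes the same section and also appears in 9(c), Local Number of Subjects. It says that "the original group size analysis of 96 (32 in each of three groups) did not account for potential loss of data" or for withdrawals, and that the request should have been for "106 subjects with the expectation of a 10% loss of data due to incomplete records or withdrawal of subjects in the study". The enrolment target in 9(c) and 9(e) is 106. Section 9(f) defines the primary endpoint as a comparison of pain relief on the VAS among the three treatment groups.

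**The concern.** The two statements give different origins for 106. One makes it the output of the power calculation. The other makes it that output, 96, plus an allowance. They cannot both be the analysable number from one calculation. If 106 analysable subjects really were needed, enrolling 106 and losing 10% would leave the trial short.

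Three further points seem to add weight:

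- The allowance looks as if it was made by multiplying by 1.10 rather than dividing by 0.90.
- The primary endpoint involves three groups, while the named tests for means compare two, so 90% might apply to a single uncorrected comparison.
- Section 9(l) withdraws subjects who do not complete the infusion, so the number analysed will probably differ from the number enrolled.

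At stake is how a null result would be read: against a power of 90% that the design might not have.

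**Working it through.** **Inputs.** From 9(i) and its note: 96 subjects, 32 per group; 10% loss; 106 to enrol; power 90%; alpha 0.05. Assumed, because the plan does not say: two-sided testing, equal groups and, where a mean difference is needed, 20 mm between groups.

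**1. Does 106 follow from 96?**
- Multiplying: 96 × 1.10 = 105.6, rounded up to 106.
- Dividing: 96 / (1 − 0.10) = 106.7, rounded up to 107, or 108 for equal thirds.
- Loss that 106 can absorb and still leave 96: 1 − 96/106 = 9.4%.

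The two methods differ by one or two subjects. The figure of 106 reproduces as an enrolment target for 96 analysable.

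**2. Power at the number expected to be analysed.** Expected number: 106 × 0.90 = 95.4, or 31.8 per group. Suppose 32 per group gives 90%. In the normal approximation the standardised signal is then 1.960 + 1.282 = 3.242. At 31.8 per group:

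3.242 × √(31.8/32) = 3.231; 3.231 − 1.960 = 1.271; power = Φ(1.271) = 89.8%.

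Calibrated in the same way, other tests agree:

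| Analysed | Normal | t test | Three-group ANOVA |
|---|---|---|---|
| 95.4 | 89.8% | 89.8% | 89.8% |
| 96 | 90.0% | 90.0% | 90.0% |
| 106 | 92.6% | 92.7% | 92.8% |

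**3. The literal reading.** If 106 analysable were required for 90%, then 95.4 analysed gives 3.242 × √(31.8/35.33) = 3.075; 3.075 − 1.960 = 1.115; Φ(1.115) = about 87%. Holding 90% would need 106 / 0.90 = 117.8, so 118 enrolled. This arithmetic is correct, but its premise conflicts with the note, which says the group-size analysis gave 96 and that 106 already contains the allowance.

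**4. Three groups.** If 32 per group gives 90% for one uncorrected t test, the standardised difference is 0.823, and each of three Bonferroni-corrected comparisons has 79.5% power. That result assumes the uncorrected test in order to obtain 0.823. The plan does not say so, and 90% at 32 per group fits other designs equally well, for a 20 mm difference where means are compared:
- one two-group t test, with SD about 24.3 mm;
- three Bonferroni-corrected t tests, with SD about 21.3 mm;
- a three-group ANOVA on 96 subjects, with effect size f about 0.37.

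**5. Can 90% be checked at all?** For a 20 mm difference in means, one two-sided comparison by the normal approximation, n per group = 2 × 3.242² × SD² / 20²:
- SD 20 mm gives 21.02, so 22 per group and 66 in total.
- SD 30 mm gives 47.3, so 48 per group and 144 in total.

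If the calculation was for the proportion achieving a 20 mm fall, no SD enters. Assumed rates of 30% against 70% give 93 in total, and 20% against 58% give 99 (no continuity correction). A total of 96 lies inside all these ranges, so the missing inputs leave 90% neither confirmed nor refuted.

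**The case for a change.** The strongest opposing case is that this is more than a difference between superseded and current text. The power sentence and the note both stand in the current revision and explain the same number differently. No new power analysis is described that could have produced 106. A reader who takes only the power sentence into a report would state a requirement that the planning record contradicts. The plan also never says which of the three-group comparisons carries the 90%, and better wording would cost nothing.

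Two parts of this stand. The attribution in the power sentence is loose, because it gives the enrolment number where the analysable number belongs. The inputs to the calculation are also absent, so its power cannot be reproduced.

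The rest does not follow. The analysable number is not in doubt, since 9(c) and 9(i) both give 96, 32 per group. The 87% and 118 figures require setting aside the note that reveals the mismatch. The 79.5% figure comes from an assumed test and an assumed correction, neither of which is in the plan. Nothing shows that the three-group power is below 90%, so a statement that it is lower would itself lack support.

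**Conclusion.** This is a clerical slip, with a gap in the record beside it, and no change to the plan follows. The enrolment target of 106 is stated consistently and follows from 96 with 10% loss. The only shortfall the documents support is from 90.0% to 89.8%, provided that 96 analysable subjects give 90% (the note attaches no power to 96) and that losses are 10% and spread evenly across groups. If losses stay at or below 9.4%, at least 96 remain.

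Anyone reporting the trial can take 96 as the analysable number and 106 as the enrolment number from the note itself. Correcting the sentence would not alter enrolment, the tests, the 90% figure or the reading of any result. The missing standard deviation, response rates, sidedness and comparison strategy limit what can be checked, but they do not show that the size or the power is wrong.

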- 2. All potential subjects will be informed that participation in the study could lead to a positive urine drug test that could remain positive for up to a month after the conclusion of the study.
- 3. Female subjects of child bearing age, will have a pregnancy test performed prior to enrollment; any subjects who are pregnant will be excluded from this project.
- 4. Each subject will be asked to grade his/her pain severity on a 100mm non-hatched visual analog scale (VAS) ranging from 0 (no pain) to 100 (worst, maximum pain).
- 5. Each subject will be asked to fill out a baseline pain questionnaire
- 6. Each subject will be placed on monitors for continuous pulse oximetry, Heart Rate, Respiratory Rate, and blood pressure every 5 minutes for the duration of the study of one hour and longer for any patient who needs continued care. The patients temperature will be taken prior to the start of the protocol..
- 7. Each subject will have an intravenous catheter placed.
- 8. Each subject will be sequentially assigned to one of three treatment groups, based on a computer-generated randomization schedule, to receive an intravenous infusion of sub-dissociative Ketamine (0.25mg/kg), sub-dissociative dose Ketamine (0.5mg/kg), or an equal amount of normal saline.
- 9. All medications will be prepared by an emergency department pharmacist and all study medication IV bags will be identical in appearance and will be administered by the emergency Page 4 of 11

Rev. 04/24/2018

department nurse caring for the patient who will be blinded to the study drug.

- 10. Each subject will receive lightly tinted sunglasses to wear during the duration of the study to minimize bias as ketamine can evoke a tell-tale short-lived nystagmus
- 11. Each subject will receive the study medication over a 20 minute period via an automated pump. At this point, the subjects will be asked to rate their pain on a VAS and asked if they need additional pain medication that will consist of intravenous hydromorphone with the dose and frequency determined by the discretion of the treating physician and documented on the data collection sheet.
- 12. After 1 hour the subject will again be asked to grade his/her pain on a VAS. Additionally, they will be asked if they experienced any other adverse effects over the treatment period, specifically: rash, hallucinations, anxiety, disorientation, burning at the injection site.

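### Section 9(l) withdraws subjects who do not complete the infusion and does not say their outcomes are still collected or analysed, so randomised subjects can be lost for an arm-related reason

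*Combined protocol and SAP*

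**What the plan says.** Section 9(l), Withdrawal of Subjects, applies one rule to all arms: "Subjects will be withdrawn from the study if they don't complete their Ketamine or normal saline infusion". The sentence goes on to say that "they will continue to be monitored and treated as necessary if they experience any untoward or unexpected effects from the medication". That promises care. It does not mention VAS ratings, rescue hydromorphone or the adverse-effect questions.

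In section 9(g), step 11 gives the study drug over 20 minutes and then says "At this point, the subjects will be asked to rate their pain on a VAS". Step 12 says "After 1 hour the subject will again be asked to grade his/her pain on a VAS" and asks about adverse effects at the same time. Step 14 is a telephone call to all subjects at 24-48 hours, using a separate pain rating scale.

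Section 9(i) names a t test, a chi-squared test and Fisher's exact test. It gives no analysis population and no rule for missing values. The 4/24/2018 modification, in sections 9(c) and 9(i), justifies "106 subjects with the expectation of a 10% loss of data due to incomplete records or withdrawal of subjects in the study".

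In section 10 the ketamine list ends with "hallucinations, rash, agitation, anxiety, fatigue, unmasking psychosis". The saline list reads "Common: None Uncommon: Edema", plus, rarely, heart failure from fluid overload.

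**The concern.** The rule withdraws people from the study, not only from treatment, on the basis of something that happens after randomisation and that treatment can influence. A subject who stops early does not reach the point at which the first post-treatment VAS is taken. If withdrawal is applied literally, that subject may also have no 1-hour VAS, no hydromorphone total and no adverse-effect answers.

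If these subjects then drop out of the analysis, the groups compared are no longer the groups randomised. Secondary endpoint (b), complications of ketamine, is the most exposed, because the people removed may be the ones with the event being counted. The VAS and hydromorphone comparisons could be biased in either direction, depending on how much relief stoppers had. The ten added subjects restore numbers but do nothing about unequal loss between arms.

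**Working it through.** **Inputs from the documents.** 96 subjects (32 per group) before loss; 106 after; 10% expected loss; 80 enrolled by 4/24/2018; three groups, taken as equal in size, so 106/3 = 35.33 per arm and 70.67 in the two ketamine arms. No stopping, complication or responder rates are given; every such rate below is an assumption.

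**The plan's own figure.** 96 × 1.10 = 105.6, rounded to 106. Dividing instead gives 96/0.90 = 106.7, or 107. So 106 reproduces to within rounding, and 106 × 0.90 = 95.4 subjects remain against the 96 wanted. The allowance protects the sample size approximately, and only that.

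**How many stoppers the allowance could contain.** 106 - 96 = 10 losses, from incomplete records and withdrawal together. Infusion stoppers could be 0 to 10 of these.
- All 10, spread evenly: 10/106 = 9.4% of each arm.
- All 10 in the ketamine arms: 10/70.67 = 14.2% of those arms.

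**Complications if stoppers are left out.** With true rate p, share stopping s, and share f of stoppers with a complication, the rate among completers is (p - f·s)/(1 - s). Assume p = 30%.

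| Stoppers | f | s = 5% | s = 10% |
|---|---|---|---|
| All have a complication | 1 | 0.25/0.95 = 26.3% | 0.20/0.90 = 22.2% |
| Half stop for one, the rest at 30% | 0.5 + 0.5 × 0.3 = 0.65 | 0.2675/0.95 = 28.2% | 0.235/0.90 = 26.1% |
| Same rate as everyone | 0.30 | 30.0% | 30.0% |

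**Responder reading of the primary endpoint (decrease of at least 20 mm).** Assume a true rate of 50% in both arms, 10% of one ketamine arm stopping and no stopping on saline. With stoppers' responder rate r, the completers' rate is (0.50 - 0.10·r)/0.90. The group sizes are 35.33 × 0.90 = 31.8 and 35.3. Let d be the spurious difference and SE its unpooled standard error. The two-sided type I error is then Φ(-1.96 + d/SE) + Φ(-1.96 - d/SE).

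| r | Completers' rate | Spurious difference | Type I error |
|---|---|---|---|
| 10% | 54.4% | +4.4 points | 6.5% |
| 50% | 50.0% | 0 | 5.0% |
| 80% | 46.7% | -3.3 points | 5.9% |

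**Continuous reading.** Suppose completers show a 20 mm difference and stoppers gain nothing over saline. With about 35 per arm, the difference in all randomised subjects is 20 × (1 - w/35) for w stoppers: 18.9 mm for w = 2 and 17.7 mm for w = 4. The extreme is w = 10, the whole loss allowance in one arm, giving 14.3 mm.

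**Missing VAS with no rule.** For m missing ratings, an arm's responder rate is uncertain by m/35.33: 2.8 points for one and 11.3 points for four. These are best-to-worst bounds, not expected biases.

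**The case against.** No passage says that non-completers are excluded from analysis. The 10% figure is a sample-size allowance; it does not mention infusion stoppers and would fit ordinary withdrawal of consent. Steps 12 to 14 are not worded as conditional on completing the infusion, and step 6 monitors each subject for an hour, so data collection may well continue. Harms have other routes into the record: section 9(l) itself keeps watching subjects with reactions, the 24-48 hour call asks about ill effects, and the Safety Monitor reviews all patient information monthly. The ketamine list is a risk disclosure with incidence unknown, not a list of reasons for stopping. The efficacy distortions calculated are small.

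Much of this stands. Exclusion is an inference, arm-dependence is plausible but not documented, and the size could be nil. Some harms probably would be recorded. What does not stand is that the text resolves the matter. It says withdrawn from the study, the modification counts withdrawal as lost data, and the follow-up call supplies neither the emergency department VAS nor the rescue total. Recording a reaction for safety oversight also does not put that subject in the denominator or numerator of an endpoint analysis.

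**Conclusion.** The concern holds. Followed as written, section 9(l) can remove randomised subjects for a reason related to their arm, and nothing elsewhere in the protocol and SAP places them back in the endpoint analyses. The clearest exposure is the complication endpoint, where a true 30% would appear as anything from 22.2% to 30% under the assumptions above. The direction is towards understatement whenever stoppers have more complications than other subjects. For pain relief the direction is open and the illustrated error is small, with type I error of 5.0% to 6.5%.

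All of these sizes rest on assumed rates and on the inference that withdrawn subjects are not analysed. Confidence in the practical impact is therefore moderate. The point deserves correction because the rule is explicit, the plan expects losses without saying how to handle them, and the remedy is cheap.

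**What to change.** **Section 9(l).** State that a subject who stops the infusion remains in the study for data unless consent is withdrawn. Take the VAS ratings at the same scheduled times as for completers, and also collect total hydromorphone, the adverse-effect answers and the 24-48 hour call. Make no change to when an infusion is stopped or to clinical care.

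**Section 9(i).** State that:
- efficacy is analysed in all randomised subjects as assigned;
- missing VAS and missing hydromorphone totals are handled by a named method, with a sensitivity analysis. For a responder endpoint this could count missing VAS as no significant relief, then the reverse. If VAS is analysed as continuous, that scale needs its own stated method;
- complications are analysed in everyone who received any study infusion;
- non-completers and their reasons are reported by arm.

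**Subjects already enrolled.** The modification reports that the investigators "have thus far enrolled 80 and the recruitment has continued on schedule". Keep all data already held on non-completers among these 80, and apply the missing-data rule to those without a VAS.

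**Cost.** One paragraph in 9(l) and a few sentences in 9(i), submitted as a further protocol modification. The consent wording on data after withdrawal should be checked, since those pages are not in the documents reviewed. No extra visits are needed, because step 6 already covers the hour and step 14 already calls everyone. Partial infusions will dilute the ketamine effect somewhat. New collection can reach at most 106 - 80 = 26 subjects; for the other 80 only the analysis and reporting rules help.
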